## 5.4 Month/year derivation

For all derivations, a year will be defined as 365.25 days and a month will be calculated as  $(365.25 / 12) = 30.4375$  days. If duration is to be reported in months, duration in days will be divided by 30.4375.

## 5.5 Body mass index

Body mass index, in  $\text{kg}/\text{m}^2$ , is a measure of relative weight based on an individual's mass and height.

It is calculated using the following formula, where weight is in kilograms and height is in meter:

$$\text{BMI} = \text{Weight} / \text{Height}^2$$

Baseline BMI will be determined using the last available height and weight prior to start of study drug.

## 5.6 Growth data

SDS will be calculated using the current formulae provided by the WHO as follows:

1. Calculate  $z_{\text{ind}} = \frac{\left(\frac{x}{m}\right)^L - 1}{s}$
2. If  $|z_{\text{ind}}| \leq 3$ ,  $SDS = z_{\text{ind}}$   
If  $z_{\text{ind}} > 3$ ,  $SDS = 3 + (X - SD3pos) / SD23pos$   
If  $z_{\text{ind}} < -3$ ,  $SDS = -3 + (X - SD3neg) / SD23neg$

where:

- $X$  is height in centimeters or BMI in kilograms/ $\text{m}^2$ ,
- $L, M$  and  $S$  are height or BMI-, sex- and age-specific reference values from the WHO Growth Charts.

- SD3pos is the cutoff 3SD calculated by the LMS method:  
$$SD3_{pos} = M * (1 + LS*3)^{1/L}$$
- SD3neg is the cutoff -3SD calculated by the LMS method:  
$$SD3_{neg} = M * (1 + LS*(-3))^{1/L}$$
- SD23pos if the difference between the cutoffs 3SD and 2SD:  
$$SD23_{pos} = M * (1 + LS*3)^{1/L} - M * (1 + LS*2)^{1/L}$$
- SD23neg if the difference between the cutoffs -2SD and -3SD:  
$$SD23_{neg} = M * (1 + LS*(-2))^{1/L} - M * (1 + LS*(-3))^{1/L}$$

Height-for-age and BMI-for-age L, M and S reference values for males and females are available under <http://www.who.int/childgrowth/standards/en/> (for patients aged between 0 to 5 years old) and <http://www.who.int/growthref/en/> (for patients aged between 5 to 19 years old). These correspond to the latest available international references available at this time and described in the 2007 Bulletin of the World Health Organization ([Mercedes de Onis et al 2007](#)). The age category immediately above the patient's exact age should be used. SDS is actually a Z score that measures the distance from the population mean in units of standard deviations. That is, SDS  $\leq -1.645$  refers to values in the lowest 5%. (The usual percentile more commonly used in the clinical practice can be derived from the z-score by a normal distribution).

Note that BMI is reported instead of weight as no reference data are provided by the WHO for age beyond 10.

Height velocity is defined as follows:

Height velocity (cm/6-months) = (height in time window  $k$  – height in time window  $k-1$ )  $\div$  ([assessment date in time window  $k$  – assessment date in time window  $k-1$ ]  $\times$  [365.25/2]),

and similarly for weight velocity.

Velocity SDS is calculated as (velocity – mean) / SD, where mean and SD are obtained as the height-, weight-, sex- and age-specific values ([Baumgartner et al 1986](#)), where the age category immediately above the patient's exact age (at the assessment date in time window  $k$ ) should be used. Velocity SDS will only be calculated for time window  $k$  if data also exists for time window  $k-1$ , since calculating across multiple units of 6 months requires more than one reference value to be taken into account.

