### 2.7.7.1 SDS method

**Growth data** collected during the study (both core and extension phases) for safety set 4 subjects will also be summarized descriptively at each relevant time point. These data consist of BMI, height, height velocity, weight and weight velocity.

The baseline for this analysis will be the core phase baseline for both DT crossover and granule patients.

Height and BMI will be summarized at 6 months intervals, using the standard deviation scores (SDS, also called z-score), velocity and velocity SDS. The relevant height and weight values for each 6-month period are defined using time windows, as defined in [Section 5.3.3](#). The z-scores will allow identification of potential outliers.

The formula used to calculate the SDS and height and weight velocities are provided in [Section 5.6](#).

Note that BMI SDS are reported instead of weight SDS as no reference data for weight are provided by the WHO for age beyond 10.

Height/BMI SDS and height/weight velocity SDS will be summarized using descriptive statistics (mean, standard deviation, range) for each time window (at Baseline and thereafter allowing informal comparison of growth data), as well as by presenting number of patients with SDS values lower/higher than 5th/95th percentiles respectively. Box plots will also be plotted for each time window. In addition, a shift table to compare baseline SDS to the worst on-treatment SDS will be produced for height and BMI SDS. All height/BMI SDS, velocity and velocity SDS data will be listed, and values of SDS and velocity SDS outside of the central 95% of population values will be flagged as either High (SDS > 1.645) or Low (SDS < -1.645).

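### The SDS formula printed in section 5.6 of the final SAP omits L from its denominator and contradicts the section's own 3 SD cut-offs, so height and BMI scores come out wrong wherever L differs from 1

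*SAP*

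**What the plan says.** The final SAP (first version, 21-Feb-2024, before database lock) describes the growth analysis in section 2.7.7.1 and gives the formulae in section 5.6.

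- **Source of the method.** Section 5.6 says "SDS will be calculated using the current formulae provided by the WHO as follows". L, M and S are "sex- and age-specific reference values from the WHO Growth Charts", and X is height or BMI. One formula serves both.
- **Step 1.** z_ind = ((x/m)^L − 1)/s, printed with lower-case x, m and s.
- **Step 2.** If |z_ind| ≤ 3, SDS is z_ind. Above 3, "SDS = 3 + (X - SD3pos) / SD23pos". Below −3, "SDS = -3 + (X - SD3neg) / SD23neg".
- **Cut-offs.** SD3pos "is the cutoff 3SD calculated by the LMS method" and equals M(1 + 3LS)^(1/L). SD3neg equals M(1 − 3LS)^(1/L). SD23pos and SD23neg are differences between the 3 SD and 2 SD points on each side and also contain LS.
- **Use.** Section 2.7.7.1 summarises height and BMI SDS by time window on Safety Set 4, counts patients beyond the 5th and 95th percentiles, draws box plots and tabulates shifts from baseline to the worst on-treatment value. It lists the data, with values "outside of the central 95% of population values will be flagged as either High (SDS > 1.645) or Low (SDS < -1.645".

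**The concern.** Steps 1 and 2 are parts of one algorithm. Step 2 changes branch at z_ind = ±3 and continues from SD3pos or SD3neg, so z_ind must equal exactly +3 and −3 at those two points. With S alone in the denominator it does not, unless L = 1.

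A programmer who codes the line literally would produce rescaled scores, or scores with the wrong sign, and could send a child to the wrong tail formula. BMI SDS stands in for weight SDS here, because the SAP notes that no WHO weight reference is provided beyond age 10. Extension-phase safety, including growth and development, is the objective marked for reporting in the final CSR (final SAP Table 1-1).

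Section 2.7.7.1 also describes ±1.645 as the limits of the central 95%. Those limits enclose the central 90%.

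**Working it through.** **Inputs.** The step 1 formula, the step 2 rule and the cut-offs come from final SAP section 5.6. The flag limits ±1.645 come from section 2.7.7.1. No values of L, M or S are given, so I assume L between −2 and 1.5 and S between 0.08 and 0.12 for illustration. M cancels.

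**1. The plan's own cut-offs.** Let X be the value at true score k, so X/M = (1 + kLS)^(1/L) and (X/M)^L = 1 + kLS.

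- As printed: z_ind = (1 + kLS − 1)/S = kL.
- With denominator L×S: z_ind = kLS/(LS) = k.

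At SD3pos (k = 3) the printed line gives 3L: −6 at L = −2, −3 at L = −1, 1.5 at L = 0.5, and 3 only at L = 1. With L×S it gives 3 at SD3pos and −3 at SD3neg for every L and S tried.

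**2. Inside the central branch (|kL| ≤ 3).** SDS = kL.

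| L | true −2 | true +2 | flags as printed |
|---|---|---|---|
| −1 | +2 | −2 | High and Low exchanged |
| −0.5 | +1 | −1 | neither flagged |
| 0.5 | −1 | +1 | neither flagged |
| 1 | −2 | +2 | correct |

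Within this branch, an exchange of flags at a true ±2 needs 2|L| > 1.645 and 2|L| ≤ 3 with L negative. That means L between −1.5 and about −0.82.

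**3. Outside the central branch (|kL| > 3).** SDS is no longer kL. Take L = −2, S = 0.10, in units of M.

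- True −2: X = 1.4^(−1/2) = 0.8452 and z_ind = (1.4 − 1)/0.10 = +4, so the upper tail formula is used. SD3pos = 0.4^(−1/2) = 1.5811. SD23pos = 1.5811 − 0.6^(−1/2) = 1.5811 − 1.2910 = 0.2901. SDS = 3 + (0.8452 − 1.5811)/0.2901 = +0.46.
- True +2: X = 1.2910 and z_ind = (0.6 − 1)/0.10 = −4, so the lower tail formula is used. SD3neg = 1.6^(−1/2) = 0.7906. SD23neg = 0.8452 − 0.7906 = 0.05458 before rounding. SDS = −3 + (1.2910 − 0.7906)/0.05458 = +6.17.

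| L = −2 | S = 0.08 | S = 0.10 | S = 0.12 |
|---|---|---|---|
| true −2 | +0.03 | +0.46 | +0.88 |
| true +2 | +5.07 | +6.17 | +7.49 |

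The low value loses its flag. The high value is still flagged High but is greatly inflated. Some values even keep the right sign: at L = −2 and S = 0.08, a true −3 gives −0.24. With L = 1.5 and S = 0.10, a true +2.9 has z_ind = 4.35 but SDS = 2.90, almost unchanged.

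**4. The ±1.645 limits.** 2 × (1 − Φ(1.645)) = 0.100, so they enclose the central 90%. This agrees with the 5th and 95th percentile counts in section 2.7.7.1 and with section 5.6, which places scores at or below −1.645 in the lowest 5%.

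**The case against.** **Possible reading loss.** Step 1 is a stacked fraction, and it shows x, m and s where the definitions use X, M and S. An L could have been lost when the text was read from the PDF. This stands: the source page has to be checked before the line is called an error in the plan.

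**Stated intent.** The SAP says it follows the WHO formulae and calls SDS a z-score in SD units, and programming specifications are kept in a separate document. The program may therefore be correct. That is fair, but the SAP writes out a formula to be followed, and as it reads that formula disagrees with the lines beneath it.

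**Stronger readings that do not hold.**

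- A reader might infer that every BMI SDS is multiplied by L, so that a true −2 at L = −2 is reported as +4. That +4 is z_ind. The tail rule then applies, and SDS is +0.03 to +0.88 over the assumed S.
- A reader might infer that negative L always flags thin children High and heavy children Low. That exchange needs particular L values, which the documents do not give.
- The fault is not confined to BMI, because height uses the same step. Velocity SDS has its own formula without L and is unaffected.

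**Importance.** This is a descriptive summary meant for informal comparison. No hypothesis test depends on it, so the consequence is limited, though the correction is still needed.

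**The 95% wording.** The numerical limits are explicit and consistent with the stated percentiles, so no output changes. Moving to ±1.96 would break that agreement.

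**Conclusion.** On the text available, section 5.6 contradicts itself. The printed z_ind is L times the value its own cut-offs require, and only the denominator L×S reconciles them. The contradiction follows from the SAP alone, but the finding is conditional on the source page showing S alone.

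If coded as printed, height and BMI SDS are wrong wherever L differs from 1, apart from values at the median and some tail values that happen to come out nearly right. The size depends on L and S, which are assumed here. Under those assumptions the results range from a lost flag, through an exchanged flag, to an inflation of a true +2 to between +5.1 and +7.5.

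The affected outputs are the height and BMI SDS summaries, percentile counts, box plots, shift tables and High/Low flags on Safety Set 4. Velocity SDS and the co-primary analyses are untouched. The documents do not show that any reported result is wrong. The central 95% phrase is a wording slip only.

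**What to change.** 1. Check the source page of section 5.6 for a character lost from the step 1 fraction.
2. If the page shows S alone, replace step 1 with z_ind = ((X/M)^L − 1)/(L×S), using the same capitals as the definitions.
3. Whatever the page shows, test the program: X = SD3pos must return exactly 3 and X = SD3neg exactly −3, using reference rows where L is not 1. If it fails, regenerate the height and BMI SDS outputs.
4. In section 2.7.7.1 change central 95% to central 90% and keep ±1.645.

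The cost is at most one formula, one number in the text and a short program check. No new data are needed.

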### 5.3.3 Growth data

Table 5-5 summarizes the time windows for growth data, where windows are centered at every 6 months after start of deferasirox. If there is more than one assessment within the time window, the last available assessment in that time window will be used. Although height and weight could be collected more frequently than every 6 months, this choice of time window length was made to reflect the degree of accuracy in the reference values (every 6 months) that will be used in the calculation of summary variables of growth (Section 2.7.7).

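### Final-CSR SAP 5.6 reads height against the next older reference age, so height SDS is biased low while a child is growing; the size depends on a table step the SAP does not clearly state

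*SAP*

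**What the plan says.** The final-CSR SAP (the one prepared before final database lock) adds a growth analysis by standard deviation scores. Section 5.6 computes height and BMI SDS from "sex- and age-specific reference values from the WHO Growth Charts" and gives one lookup rule: "The age category immediately above the patient's exact age should be used". It mentions neither interpolation nor the nearest age. It also calibrates the score: an SDS at or below −1.645 "refers to values in the lowest 5" percent.

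For velocity, the formula is "Velocity SDS is calculated as (velocity – mean) / SD". The same round-up rule is repeated there, applied to the child's age at the assessment that closes the interval. The velocity reference is a different source, a set of published incremental growth tables.

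Section 5.3.3 justifies the 6-month analysis windows: "this choice of time window length was made to reflect the degree of accuracy in the reference values (every 6 months". It does not say whether this describes the WHO L, M, S tables, the velocity tables or both.

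Section 2.7.7.1 lists the outputs: "Height and BMI will be summarized at 6 months intervals, using the standard deviation scores (SDS, also called z-score), velocity and velocity SDS". "The baseline for this analysis will be the core phase baseline for both DT crossover and granule patients". Values above +1.645 are flagged High and values below −1.645 Low, patients beyond the 5th and 95th percentiles are counted, and "a shift table to compare baseline SDS to the worst on-treatment SDS will be produced for height and BMI SDS".

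**The concern.** Median height rises with age until growth stops. If the reference age is always rounded up, a growing child is always measured against a somewhat older and taller reference, never a younger one. The error is therefore one-sided and does not average out across children. Its size is the growth expected over the age offset, divided by the reference SD, so it falls to zero at adult height.

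Two things follow for height. First, the ±1.645 cut-offs no longer mark 5% in each tail for growing children: too many are flagged Low and too few High. Second, a child who ages during the study loses some of the bias between baseline and a later window, which adds an apparent change in SDS that is not real. Entry age is 2 to under 18 years, and follow-up is 48 weeks plus up to 5 years, about 0.92 + 5 = 5.9 years, so this drift has time to appear. Growth is a listed safety assessment for the extension phase.

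**Working it through.** **Inputs from the documents.** Round-up rule, WHO reference and −1.645 cut-off (5.6); 6-month reference accuracy, table not named (5.3.3); entry age and follow-up (protocol summary and protocol 6.1.2).

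**Inputs assumed.** The documents give no height velocity or reference SD. The values below are assumptions, with a central value and a range.

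**The SAP's own figure.** Φ(−1.645) = 0.04998, so the stated lowest 5% is reproduced when the lookup age is right.

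**Formulas.** For a step of w years, the offset runs from 0 to w and averages w/2.

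- Mean bias = −(velocity × w/2) / SD.
- Share flagged Low when true SDS is N(0,1) = Φ(−1.645 − bias).
- Share flagged High = 1 − Φ(1.645 − bias).

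With 6-month steps, w/2 = 0.25 year. Example at 2–3 years: −(8.5 × 0.25)/3.4 = −0.625, and Φ(−1.645 + 0.625) = 15.4%. The low end of each bias range pairs the lowest velocity with the highest SD; the high end does the reverse.

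| Age | Velocity, cm/yr (assumed) | SD, cm (assumed) | Mean bias, 6-month steps | Flagged Low, 6-month steps | Mean bias, monthly steps |
|---|---|---|---|---|---|
| 2–3 | 8.5 (7–10) | 3.4 (3.0–3.8) | −0.63 (−0.46 to −0.83) | 15.4% (11.8–20.8) | −0.10 (−0.08 to −0.14) |
| 5–6 | 6 (5–7) | 4.8 (4.4–5.2) | −0.31 (−0.24 to −0.40) | 9.1% (8.0–10.6) | −0.05 |
| 9–10 | 5.3 (4.5–6) | 6.2 (5.8–6.6) | −0.21 (−0.17 to −0.26) | 7.6% (7.0–8.3) | −0.04 |
| Pubertal spurt | 7.5 (6–9) | 7.5 (7–8) | −0.25 (−0.19 to −0.32) | 8.2% (7.2–9.3) | −0.04 |
| 17–18 | 0.7 (0–1.5) | 7 (6.3–7.6) | −0.03 (0 to −0.06) | 5.3% (5.0–5.6) | −0.004 |

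The monthly column is the 6-month column divided by six. Individual errors run from zero to twice the mean.

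**A second set of assumed values** gives the same picture with 6-month steps:

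- Age 3: 7.5 × 0.25/3.7 = 0.51, so bias −0.51.
- Age 8: 5.75 × 0.25/5.75 = 0.25, so bias −0.25.
- Age 17: 0.8 × 0.25/7 = 0.03, so bias −0.03.
- Tails at age 8: Low Φ(−1.645 + 0.25) = 8.2%; High 1 − Φ(1.645 + 0.25) = 2.9%. Each should be 5%.

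**Apparent change in height SDS with no true change, 6-month steps (central values):**

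- 2–3 to 5–6 years: +0.31.
- 5–6 to 9–10 years: +0.10.
- 9–10 years into the spurt: −0.04.
- Spurt to 17–18 years: +0.23.
- Age 3 to 8 on the second set: 0.51 − 0.25 = +0.26.

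With monthly steps, each is one sixth: for example, +0.05 from 2–3 to 5–6 years.

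**After the fix.** With interpolation to exact age, the offset is zero and 5.0% fall at or below −1.645. With the nearest reference age, the mean offset is about zero and the individual error is at most half a step either way.

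**The case against.** The strongest objection is about the step. The 6-month remark sits in a section on time windows and names no table. The other explicit 6-month unit, in 5.6, concerns velocity, which has a different source. If the L, M, S tables are monthly, the mean bias is about −0.1 at ages 2–3 and about −0.05 or smaller from age 5, which has little practical effect. This stands, and the size must be stated as conditional.

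The SAP also does not define a category. If categories were intervals labelled by their upper limit, the rule could pick the interval that contains the child, and the mean bias could be near zero. The SAP does not say so, and its plain wording points to an older age; the labelling should be stated.

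The analysis is descriptive, the same rule applies to all patients, and randomization was stratified by age, so an arm contrast would be little affected. Section 4 of the SAP says no comparison between the crossover and granule groups is planned for the entire granule period. Raw growth velocity is also reported without a reference table (2.7.7), and over-flagging low height is the cautious direction for a safety screen. All this limits the harm. It does not protect the within-group trend or the percentile counts, which are what will be read.

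A reader might go further and infer that every growth SDS is biased low, that the bias fades steadily with age, or that it would pass for catch-up growth and hide real impairment. The documents do not support these readings. The sign for BMI follows whether reference BMI is rising or falling at that age. For velocity, a later reference may be lower, and the interval labelling of the cited tables is not given. In the working, the bias does not fade from 9–10 years into the pubertal spurt. A drift large enough to mask impairment needs the 6-month step, which is not established for the height tables.

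**Conclusion.** The point holds for height SDS, and it is minor. On the plain reading of 5.6, the rule builds in a downward bias while a child grows, which departs from the SAP's own 5% calibration and does not fully cancel in change from baseline. That much follows from the text and from the fact that height rises with age and then stops.

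The size rests on three things the documents leave open: the table step, the growth rates and the reference SDs. Under the assumed values, the bias is material with 6-month steps and small with monthly steps. That it is largest at ages 2–3 depends on the assumed values, but it holds across their whole range. Extra Low flags and fewer High flags are a finding for height only. For BMI and velocity SDS, the documents support only that the reference age is misaligned, not the direction of any bias.

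**What to change.** In 5.6, replace the round-up rule: evaluate L, M and S at the child's exact age on the assessment date by linear interpolation between adjacent reference ages, or use the nearest reference age. State the step and labelling of each reference table, and make clear in 5.3.3 which table the 6-month remark describes. For velocity SDS, use the reference interval that best matches the child's own measurement interval.

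The cost is a short text change and a few lines of programming. No new data are needed: age from date of birth and sample date is already derived for creatinine clearance in 5.2.1.
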